#### 25.2.3 Secondary Outcomes

- i) To identify any barriers to patient recruitment and retention, and
- ii) To obtain data that will in the future allow to design a larger randomised controlled trial.

#### 25.2.3.1 Secondary Outcome 1: To identify any barriers to patient recruitment and retention

To identify any barriers to patient recruitment and retention the following wil be calculated:

- 1. Monthly registration rate.
- 2. The proportion of patients completing the study retention rate, and reasons for non-completion.

#### 25.2.3.1.1 Derivation

The monthly registration rate will be calculated as:

[the number of participants registered]/[the number of months of recruitment].

The retention rate will be calculated for day 120 and day 180 completion as:

[the number of participants to have completed\* the study]/[the number of participants registered].

\*Study completion is defined as completing the follow up visit 5 (at day 120) and telephone follow up 5 (at day 180) for completion at day 120 and day 180 respectively.

#### 25.2.3.1.2 Analysis

The total number of participants registered, the total number of months of recruitment and the number of patients completing the study visits at day 120 and day 180 will be reported overall and by site.

The monthly registration rate and the retention rate will be reported overall and by site. Reasons for non-completion including withdrawal and safety reasons will be reported.

### 25.2.3.2 Secondary Outcome 2: To obtain data that will enable a larger randomised controlled trial to be designed in the future

To obtain data that will enable a larger randomised controlled trial to be designed in the future, the following will be assessed:

1. Change of pain intensity measured on a 0-10 point NRS from baseline (0 day) to 4 months/120 days after completion of Anakinra administration. Pain intensity at 120 days is defined for the purpose of this study a mean of the weekly scores and daily over the last month of drug administration. This is determined by calculating the results of the patient pain diaries.

- 2. CRPS severity score,
- 3. Global assessment of change,
- 4. Analgesic Medication use,
- 5. EQ-5D 5L
- 6. PHQ-9
- 7. BPI
- 8. HADS
- 9. Skin sensitivity measured by mechanical QST
- 10. Limb Volume (Figure of 8)
- 11. Work status

Table 25-1 details the timepoints and CRFs where each outcome measure is collected.

**Table 25-1 Secondary outcome collection** 

Outcome	Timepoint (Days)	CRF
Pain intensity on 10-point NRS	0	Form 4: Baseline
	120	INCA CRPS Severity Score
		Pain diaries day 93 to 120
CRPS Severity score	0, 30, 60, 90, 120	INCA CRPS Severity Score
		Pain diaries
Global assessment of change	120	
Analgesic Medication use	0, 120	Concaminant medication use
EQ-5D 5L	0, 30, 60, 90, 120, 180	INCA EQ-5D 5L
PHQ-9	0, 30, 60, 90, 120	INCA PHQ-9 Questionnaire
BPI	0, 30, 60, 90, 120	INCA BPI
HADS	0, 30, 60, 90, 120	INCA HADS
Skin sensitivity measured by mechanical QST	0, 120	INCA Quantative Sensory Testing
Limb volume (figure of 8)	0	Form 1: Screening
	60, 120	Form 6: Follow up
Work status	0	Form 4: Baseline
	120	Form 6: Follow up

## 25.2.3.2.1 Change of pain intensity measured on a 0-10 point NRS from baseline (0 day) to 4 months/120 days after completion of Anakinra administration.

Pain intensity at 120 days is defined for the purpose of this study as mean of the weekly scores and daily scores over the last month of drug administration. This is determined by calculating the results of the patient pain diaries.

#### 25.2.3.2.1.1 Derivation

The total weekly score will be calculated as the total NRS score per week for days 93 to 120 (last 4 weeks, inclusive of days 93 and 120) from the patient pain diaries. The mean of the total weekly scores (average weekly score) per patient will be calculated as:

[sum of total weekly scores for days 93 to 120 (inclusive)]/ 4.

The mean daily average over the last month per patient will be calculated as:

[sum of the scores for days 93 to 120 (inclusive)]/28.

The change in score will be the weekly and daily average at day 120 minus the baseline score. The baseline score is collected on Form 4: Baseline and is the average pain from CRPS over the last 24 hours at baseline.

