#### 15.2 Secondary outcomes

To identify any barriers to patient recruitment and retention:

- 1. Monthly registration rate.
- 2. The proportion of patients completing the study retention rate, and reasons for non-completion.

To obtain data that will enable a larger randomised controlled trial to be designed in the future:

- 3. Change of pain intensity measured on a 0-10 point NRS from baseline (0 day) to 4 months/120 days after completion of Anakinra administration. Pain intensity at 120 days is defined for the purpose of this study as a mean of the weekly scores and daily over the last month of drug administration. This is determined by calculating the results of the patient pain diaries.
- 4. CRPS severity score
- 5. Global assessment of change
- 6. Analgesic Medication use
- 7. EQ-5D 5L
- 8. Patient Health Questionnaire 9 (PHQ-9)
- 9. Brief Pain Inventory (BPI)
- 10. Hospital anxiety and depression scale (HADS)
- 11. Skin sensitivity measured by mechanical quantitative sensory testing (QST)
- 12. Limb Volume (Figure of 8)
- 13. Work status

LIVERPOOL CLINICAL TRIALS CENTRE LCTC

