#### 25.1.2.4 Futility

The average CRPS pain over the 2 weeks prior to visit 5 (day 120) will be calculated using the Pain diaries days 106 to 119 whereby the average will be:

[the sum of the completed days 106 to 119]/ [number of completed entries].

The baseline pain score, ranging from 0 to 10, is collected on Form 4: Baseline as the average pain from CRPS over the last 24 hours. The average difference will be calculated as the average pain over the 2 weeks prior to visit 5 – baseline measure (day 0). The difference will then be classified for each participant as  $\geq$  2 points of pain reduction on the NRS (rounded to the nearest whole number) or less than 2 points of pain reduction on the NRS, including an increase in score.

After 12 participants have been recruited and completed 4 months treatment period the criteria is met if both of the below are met:

- An average of no pain increase among the completed patients
- At least one participant reporting at least 2 points of pain reduction on the NRS

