#### 25.2.3.2.1.2 Analysis

Continuous data will be summarised using mean, SD, median, IQR, maximum and minimum value. Summaries will be provided for:

- Baseline score
- Average weekly scores (days 93 to 120)
- Daily average over the last month (days 93 to 120)
- Change in scores for weekly and daily average at day 120 from baseline.

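### The SAP's weekly change in pain subtracts a 0-10 baseline rating from an average of seven-day totals (0-70), so it is not a change on the 0-10 NRS

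*SAP*

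**What the plan says.** SAP 15.2 names the outcome as "Change of pain intensity measured on a 0-10 point NRS from baseline (0 day") to day 120. The introduction to it in SAP 25.2.3.2.1 describes day-120 pain as a mean of diary scores over the last month of treatment.

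SAP 25.2.3.2.1.1 turns this into two quantities:

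- **Weekly version.** "The total weekly score will be calculated as the total NRS score per week for days 93 to 120". The average weekly score is then "sum of total weekly scores for days 93 to 120 (inclusive)]/ 4".
- **Daily version.** The daily average is "sum of the scores for days 93 to 120 (inclusive)]/28".

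Both are compared with the same baseline: "The change in score will be the weekly and daily average at day 120 minus the baseline score". On that baseline the section says: "The baseline score is collected on Form 4: Baseline and is the average pain from CRPS over the last 24 hours at baseline". The futility section (SAP 25.1.2.4) confirms its scale: "The baseline pain score, ranging from 0 to 10, is collected on Form 4: Baseline".

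SAP 25.2.3.2.1.2 commits to summarising both results, listing "Change in scores for weekly and daily average at day 120 from baseline" without ranking one above the other. Protocol 10.7 sets the diary to weekly entries up to day 90, daily entries from day 90 to day 120, and weekly entries again to day 180.

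**The concern.** A change score needs both terms on the same scale. Here the first term of the weekly version is an average of sums of seven ratings, and the second is one rating. Nothing in either document divides the weekly total by seven or multiplies the baseline by seven.

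The stake is the use of the result. Protocol 14.2 says that change in NRS pain is the main outcome that will feed later studies and inform their sample size. A mean and SD from the weekly line could not serve that purpose. They mix seven times the final pain level with one times the baseline, so they do not describe how much pain changed.

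**Working it through.** **Inputs**

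- Window: days 93 to 120 inclusive (SAP 25.2.3.2.1.1). The SAP's own figures reproduce: 120 - 93 + 1 = 28 days = 4 weeks of 7 days, which matches the divisors 4 and 28.
- Diary frequency in the window: daily (Protocol 10.7), so 7 ratings per week, each 0-10.
- Baseline b: one 24-hour rating, 0-10 (SAP 25.2.3.2.1.1 and 25.1.2.4).
- Plausible values of b: about 6 to 10. Protocol 7.1 requires a pre-baseline diary mean of at least 6. The Form 4 rating is a separate measurement, so this range is a guide and not a bound.

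**Formulas**

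Let S be the sum of the 28 daily ratings and m = S/28 the daily mean.

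- Average weekly score = S/4 = 7 x S/28 = 7m. Range: 7 x 0 = 0 to 7 x 10 = 70.
- Daily change = m - b.
- Weekly change = 7m - b = (m - b) + 6m.

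The last form shows the size of the distortion: the weekly change exceeds the true change by six times the final pain level.

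**Results**

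| Baseline b | Daily mean m | Daily change m - b | Weekly change 7m - b |
|---|---|---|---|
| 6 | 6 | 0 | 42 - 6 = +36 |
| 6 | 3 | -3 | 21 - 6 = +15 |
| 7 | 7 | 0 | 49 - 7 = +42 |
| 7 | 5 | -2 | 35 - 7 = +28 |
| 7 | 4 | -3 | 28 - 7 = +21 |
| 7 | 1 | -6 | 7 - 7 = 0 |
| 8 | 4 | -4 | 28 - 8 = +20 |
| 8 | 2 | -6 | 14 - 8 = +6 |
| 8 | 0.8 | -7.2 | 5.6 - 8 = -2.4 |
| 10 | 5 | -5 | 35 - 10 = +25 |

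**Where the sign turns.** 7m - b < 0 requires m < b/7, a fall of more than 6/7 = 85.7%. The daily mean would have to be below 0.86 for b = 6, below 1.14 for b = 8 and below 1.43 for b = 10.

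**Where the value leaves the scale.** The largest possible worsening on a 0-10 scale is 10 - b. The weekly change exceeds it when 7m - b > 10 - b, that is, when m > 10/7 = 1.43.

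**Effect on the SD (illustration; the inputs are assumptions, not in the documents).** Take SD 2 for m and 1.2 for b, with correlation r from 0 to 0.8.

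- Weekly variance = 49 x 4 + 1.44 - 2 x 7 x r x 2 x 1.2 = 197.44 - 33.6r. The SD is 14.1 at r = 0 and 13.1 at r = 0.8.
- Daily variance = 4 + 1.44 - 4.8r = 5.44 - 4.8r. The SD is 2.3 at r = 0 and 1.3 at r = 0.8.

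**After correction.** Using the mean of each week's ratings, the average of four weeks is 7m/7 = m. The change from 8 to 4 is then -4 and the change from 6 to 3 is -3, the same as the daily version.

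**The case against.** The case for leaving this alone is that it does little harm.

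- The correctly scaled daily change is derived in the same section and reported in the same list. With complete diaries, the planning figure that Protocol 14.2 wants is there.
- No decision uses the weekly change. The primary outcome is safety, the protocol states no formal hypotheses, and the futility criterion has its own derivation on 0-10.
- From a baseline of 7 the largest possible worsening is +3, so +21 or +42 is visibly impossible. The error can be undone by dividing the weekly average by 7, with no loss of data.

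All of this stands, and it limits the seriousness. It does not make the stated derivation right: an analyst who programs the SAP as written reports a wrong number.

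A second defence is that a weekly score might be one separate weekly rating, in which case dividing by 4 would give a 0-10 mean. The diary form is not in the documents, so this cannot be excluded outright. It fits poorly. The protocol schedules daily entries in this window, and the SAP speaks of a total per week.

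A reader might also infer stronger things that the documents do not support:

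- *That even a large improvement will be reported as severe worsening.* The SAP attaches no label of better or worse to the number, and for falls above about 86% the value is negative.
- *That the weekly and daily signs always conflict.* They conflict only for falls short of that threshold. If pain rises, both are positive.
- *That no change of divisor would cure it.* Dividing the sum of the weekly totals by 28, or by the number of completed entries as the futility derivation does, would restore the 0-10 scale.

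**Conclusion.** The weekly change is wrong as written: the two terms are on different scales, and nothing elsewhere in the SAP or protocol rescales them. It overstates the change by six times the final daily mean, for example by 24 points when that mean is 4.

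The error is contained. It affects one descriptive line of a secondary outcome, which carries no information beyond the daily line when the diary is complete. It should be fixed before analysis, because pain change is meant to plan the next trial and the SAP does not say which version to use. It does not threaten the primary outcome or any progression decision.

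The conclusion assumes that the weekly totals are built from the daily diary ratings that Protocol 10.7 specifies. The worked values also assume all 28 entries are present. The factor of seven between the two averages follows from the divisors 4 and 28 whenever both use the same entries. The treatment of blank diary days is a different question and is not needed for this point.

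**What to change.** Preferred: delete the weekly-total version and its change from SAP 25.2.3.2.1.1, and the corresponding lines from 25.2.3.2.1.2, leaving the daily mean as the single day-120 pain measure. With complete diaries nothing is lost. The description of the outcome in SAP 15.2 and 25.2.3.2.1, which refers to weekly as well as daily scores, should be aligned with this.

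Alternative, if the weekly version is kept: define each weekly score as the mean of that week's daily ratings (0-10), average the four weekly means, and then subtract baseline. With complete diaries this gives the same values as the daily version, which is why deletion is cleaner.

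Cost: a short edit to the SAP and a line of code. No new data and no change to trial conduct are needed.

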10.7 Schedule for Assessments and Follow-up

All assessments and follow up are to be conducted in line with the Schedule of Assessments below: *Table 4: Schedule of Assessments:*

				Visit 1	Telephone follow up 1	Visit 2	Telephone follow up 2	Visit 3	Telephone follow up 3	Visit 4	Telephone follow up 4	Visit 5	Telephone follow up 5	
		Screening	Pre-baseline Telephone visit	Baseline^	Baseline +2wks	Day 30*	Day 30 +2wks	Day 60*	Day 60 +2wks	Day 90*	Day 90 +2wks	Time Point Day 120*	Day 180#	Premature Discontinuation
Proced	ures													
Signed Form	Consent	Х												
Registr	ation			Х										
Assess Eligibili	ment of ty Criteria	Х		Χ										
History	of Medical (including raphics)	Χ												
Review Concor Medica	mitant	Χ		Х	X	X	Х	Х	Х	Х	Х	Х	Х	х
(Daily a	ntervention after e to day			Х		Х		Х		Х		Х		
	Medical History and examinati on	Х										Х		X***
Clinical Assessment	CRPS History and Limb Examinat ion	Х										Х		X***
Clinical	Vital signs, weight, height, HR and BP	Х		Х		Х		X		Х		Х		X***
	Limb Volume	Х						Х				Х		
applica	or Blood	Х				Х		Х		х		х		
(CXR)	Radiograph and TB testing†	Х												

				Visit 1	Telephone follow up 1	Visit 2	Telephone follow up 2	Visit 3	Telephone follow up 3	Visit 4	Telephone follow up 4	Visit 5	Telephone follow up 5	
		Screening	Pre-baseline Telephone visit	Baseline^	Baseline +2wks	Day 30*	Day 30 +2wks	Day 60*	Day 60 +2wks	Day 90*	Day 90 +2wks	Time Point Day 120*	Day 180#	Premature Discontinuation
TB scre	ening skin test†	Х												
Issue and coll	pain diary lection	Х		Х		Х		Х		Х		Х		
Numerio Score Pain	cal rating for CRPS	Х	Х	X	×	X	X	X	X	X	X	Х	Х	Х
CRPS score	Severity			Х		Х		Х		Х		Х		
EQ5D-5	5L			X		Х		Χ		Х		Х	X	
PHQ-9				Х		X		Χ		Χ		Х		
HADS				X		X		Χ		X		X		
BPI				X		X		Х		Х		X		
Work S	tatus			Х								Х		
QST-bli unblinde				Х								X+		
Global of Chan	Impression ige											Х		
Assessi Adverse	ment of Events			Х	Х	Х	X	Х	Х	Х	Х	Х	Х	Х
Blood sample collection	Clinical Chemistr y/ Hepatic Function	X				Х		X		X		X		X
Blo	Haematol ogy	Х				Х		Х		Х		Х		х
Serology	HIV/Hep atitis B and C‡	х												
Researd	ch Blood	X			/ 6							X~		

Each Time point for follow up schedule can be +/- 3 days.

†unless a TB screen of either method listed has been done in the 3 months prior to the screening visit ‡unless a screen has been done in the 3 months prior to the screening visit

[^]Time between Screening and Baseline should be no more than 14 days.

^{*} Face to face appointment

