#### 22 Analysis Datasets

#### 22.1 Efficacy Analyses

The primary and secondary outcome analyses will be conducted on all registered participants and for whom the outcome(s) of interest have been observed/measured. Patients who withdrew consent for trial continuation will contribute outcome data up until the point of withdrawal unless the patients' specifically request that the data are not to be used. No imputations will be made.

The membership of the analysis set for each outcome will be determined and documented and reasons for participant exclusion will be given prior to analysis. Reasons may include missing data, loss to follow up.

A per protocol analysis will not be performed, instead the occurrence of each protocol deviation will be monitored and sensitivity analysis performed as appropriate with patients experiencing deviations

of concern removed. The sensitivity analysis will apply to a secondary analysis of the primary outcome only.

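### The day-120 pain mean has a fixed divisor of 28 and no rule for blank diary days, so a partly filled diary run through it as written shows a false fall in pain

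*SAP*

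**What the plan says.** SAP 25.2.3.2.1.1 derives pain at day 120 from the diaries in two ways. The daily average is "sum of the scores for days 93 to 120 (inclusive)]/28". The weekly average is "sum of total weekly scores for days 93 to 120 (inclusive)]/ 4". Then: "The change in score will be the weekly and daily average at day 120 minus the baseline score". The section does not say what happens when a day is blank, and it sets no minimum number of entries.

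SAP 25.1.2.4 uses the same diaries for the futility criterion, but there the mean is "the sum of the completed days 106 to 119]/ [number of completed entries".

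SAP 22.1 restricts each analysis to registered participants "for whom the outcome(s) of interest have been observed/measured" and states "No imputations will be made". The same section says "Patients who withdrew consent for trial continuation will contribute outcome data up until the point of withdrawal", unless the participant asks for the data not to be used. Protocol 14.4.5 plans complete-case analyses and leaves the detail to the SAP.

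Protocol 10.7 has the diary filled in daily from day 90 to day 120 and weekly from day 120 to day 180. Protocol 14.2 names change in NRS pain as the main outcome contributing data to later studies, and says it will inform the next sample size.

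**The concern.** The divisor is right only for a complete diary. With any blank day the formula stops being a mean of what the participant recorded. If the blank is skipped in the sum and kept in the divisor, it has the same effect as an entry of no pain. That is imputation in all but name, and it sits against the no-imputation statement in SAP 22.1. It also sits against SAP 25.1.2.4, whose divisor shows that blank days were foreseen.

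The error runs in one direction. Blanks can only lower the day-120 score, so they can only make the change look more favourable. There is no control arm in which the artefact could cancel. The quantity affected is the one meant to inform the size of the next trial, where an exaggerated fall leads to too small a study.

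**Working it through.** **Inputs.** Window of days 93 to 120 and divisors 28 and 4 (SAP 25.2.3.2.1.1). Entry pain averaging 6 or more on a 0-10 scale (Protocol 7.1), hence the illustrative levels 6, 7 and 8. Sample size 30 (Protocol 14.2). The documents give no completion rate, so a range is shown.

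**The plan's own figure.** 120 - 93 + 1 = 28 days = 4 × 7. The divisors 28 and 4 are correct for a full diary.

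**With blanks.** Let m be the mean of the recorded scores and k the number of blank days. The sum is m(28 - k), so the formula returns m(28 - k)/28. The mean of completed entries is m. The artefact is -mk/28.

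| Unchanged pain m | k = 1 | k = 3 | k = 7 |
|---|---|---|---|
| 6 | -0.21 | -0.64 | -1.50 |
| 7 | -0.25 | -0.75 | -1.75 |
| 8 | -0.29 | -0.86 | -2.00 |

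At m = 7 the scores returned are 7 × 27/28 = 6.75, 7 × 25/28 = 6.25 and 7 × 21/28 = 5.25. Dividing by completed entries returns 7.00 and a change of 0 each time.

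**A withdrawal.** A participant with constant pain of 9 who withdraws after day 106 has 14 entries. The formula gives 9 × 14/28 = 4.5, an apparent improvement of 4.5 points.

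**Group level.** At m = 7 and completion p, the false mean fall is 7(1 - p): 0.35 at 95%, 0.70 at 90%, 1.40 at 80%.

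**Weekly version.** It returns m(28 - k)/4. At m = 7 that is 49 for a full diary and 36.75 with 7 blanks, the same proportional loss. The weekly total runs from 0 to 70 while baseline runs from 0 to 10, so flat pain of 7 gives 49 - 7 = +42 even with no blanks. That scale mismatch is a separate matter, but the repair below removes it too.

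**Only full diaries admitted.** Assuming days are independent, the share of participants with all 28 entries is p to the power 28: 75% at p = 0.99, 57% at 0.98, 24% at 0.95. Of 30 participants that is about 23, 17 and 7.

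**Effect on sizing (illustration).** Assume baseline 7, a true fall of 1.0, SD 2, two-sided 5% and 90% power, with n per arm = 2(1.96 + 1.2816)² × SD²/fall².
- Correct fall of 1.0: n = 85.
- Average of 1 blank day: apparent fall 1.0 + 6 × 1/28 = 1.21, n = 58, true power 77%.
- Average of 3 blank days: apparent fall 1.0 + 6 × 3/28 = 1.64, n = 32, true power 52%.

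This holds the SD fixed. Uneven completion would widen it and offset part of the effect on n. The bias in the mean remains.

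**The case against.** The strongest defence is that SAP 25.2.3.2.1.1 never says a blank is scored 0. Read with SAP 22.1 and Protocol 14.4.5, a 28-day sum with missing terms could be taken as missing, and the participant left out. That much stands: whether blanks act as zeros depends on how incomplete diaries are programmed. It does not rescue the text, because the SAP nowhere says that fewer than 28 entries means not observed, and it keeps data up to withdrawal. The two readings give different results and the SAP does not choose between them.

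It is also fair that this is one descriptive secondary outcome in a study with no formal hypotheses. NRS pain on the CRPS severity form (SAP 25.2.3.2.2) and BPI pain items (SAP 25.2.3.2.7) are summarised separately, and the extent of missing critical data will be reported (Protocol 14.4.2). These limit the harm. They do not correct the score.

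Three stronger inferences are not supported:
- A reader might infer that blanks arise even with perfect compliance, since "Each Time point for follow up schedule can be +/- 3 days" allows the last treatment visit on day 117. This assumes entries stop when the diary is collected. Table 4 lists both issue and collection of diaries at day 120, and the diary continues weekly to day 180.
- A reader might infer that eight blank days at pain 7 (7 × 8/28 = 2.0) create a false responder. The 2-point reduction belongs to the futility criterion, which divides by completed entries.
- A reader might infer that requiring full diaries would remove nearly everyone. At 98% or 99% completion more than half remain, and if missed days cluster within participants, more diaries would be complete at the same average rate.

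**Conclusion.** The point holds as a defect in a stated formula. Run as written on a partly filled diary, it lowers the day-120 score by mk/28 and biases the change towards benefit: 0.25 points per blank day at pain 7. The formula is inconsistent with the SAP's own no-imputation statement and with its futility mean. The alternative of admitting only full diaries is unstated and could lose many of the 30 participants.

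The existence of the bias rests on two conditions: that some diaries have blanks, and that the program sums what is there and divides by 28. Its actual size is unknown because no completion rate is given. The shares of full diaries assume independent days. The sizing example assumes its SD, fall and baseline.

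The primary safety outcome and the progression criteria do not use this formula. The mean change that Protocol 14.2 takes forward to the next trial does, so the text should be corrected before the final analysis.

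**What to change.** In SAP 25.2.3.2.1.1:

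1. Divide the daily sum by the number of completed entries in days 93 to 120, as SAP 25.1.2.4 already does for its own window.
2. Replace the weekly totals over 4 with the mean of completed entries within each week, averaged over weeks with data. Changing the 4 alone would not repair blanks inside a week.
3. Pre-specify a minimum number of entries below which the outcome is missing. The number is for the sponsor to choose; 14 of 28 is only an example and has no basis in the documents. This also defines when a diary outcome counts as observed under SAP 22.1.
4. Report the number of entries per participant.

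The cost is a few lines of SAP text and code, with no new data. The downside is that participants with few entries become missing. Dividing by completed entries also still treats the recorded days as representative of the blank ones, which is why the entry counts should be shown.
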